#### Received cardiac output monitoring (control group only)

- Deviation occurs if:
  - "Did the patient receive cardiac output monitoring during the trial intervention period" is answered "Yes"
- Deviation does not occur if either:
  - "Did the patient receive cardiac output monitoring during the trial intervention period" is answered "No"
- Deviation missing if:
  - "Did the patient receive cardiac output monitoring during the trial intervention period" is missing

#### Reasons for protocol deviations

Reasons for protocol deviations will be taken from the protocol deviation form. Reasons will only be reported for protocol deviations that occur according to one of the conditions above. If a protocol deviation form is not completed and one of the above conditions for a protocol deviation is met, we will still consider a protocol deviation to have occurred, however the reason will be missing.

# Appendix 3: Stata code for analysis

Code for analysis is written to be implemented in Stata 14, with the exception of the analysis estimating the effect of the intervention for participants who undergo surgery, which requires Stata 15 to be implemented.

# **Analysis of primary outcome**

```
mkspline age_spline = age, cubic nknots(3)
mkspline haemoglobin_spline = haemoglobin , cubic nknots(3)
mkspline creatinine_spline = creatinine , cubic nknots(3)

melogit postopinfec_30 i.treat ///
    i.plan_surg_proc i.asa_grade ///
    age_spline* haemoglobin_spline* creatinine_spline* gender ///
    || country:, or
```

#### **Analysis of secondary outcomes**

#### Mortality within 180 days of randomisation

```
mkspline age_spline = age, cubic nknots(3)
mkspline haemoglobin_spline = haemoglobin , cubic nknots(3)
mkspline creatinine_spline = creatinine , cubic nknots(3)

melogit mortality_180 i.treat ///
    i.plan_surg_proc i.asa_grade ///
    age_spline* haemoglobin_spline* creatinine_spline* gender ///
    | | country:, or
```

#### Acute cardiac event within 30 days of randomisation

```
mkspline age_spline = age, cubic nknots(3)
mkspline haemoglobin_spline = haemoglobin , cubic nknots(3)
mkspline creatinine_spline = creatinine , cubic nknots(3)

melogit ac_cardiac_30 i.treat ///
        i.plan_surg_proc i.asa_grade ///
        age_spline* haemoglobin_spline* creatinine_spline* gender ///
        | | country:, or
```

#### Acute kidney injury within 30 days of randomisation

# Acute cardiac event within 24 hours of randomisation

#### **Analysis of process measures**

#### Duration of hospital stay

```
mkspline age_spline = age, cubic nknots(3)
mkspline haemoglobin_spline = haemoglobin , cubic nknots(3)
mkspline creatinine_spline = creatinine , cubic nknots(3)

stset duration_hosp, failure(discharge)
stcrreg i.treat ///
    i.plan_surg_proc i.asa_grade ///
    age_spline* haemoglobin_spline* creatinine_spline* gender /// ///
    ,compete(death_hosp) vce(cluster country)
```

#### Number of critical care free days up to 30 days from randomisation

#### Subgroup analysis

```
mkspline age spline = age, cubic nknots(3)
mkspline haemoglobin_spline = haemoglobin , cubic nknots(3)
mkspline creatinine spline = creatinine , cubic nknots(3)
*fitting model including interaction term
melogit postopinfec 30 i.treat##i.plan surg proc i.asa grade ///
      age spline* haemoglobin spline* creatinine spline* gender ///
       || country:, or
est store A // storing estimates
*Obtaining treatment effects for subgroups
lincom 1.treat + 1.treat#2.plan surg proc, eform
lincom 1.treat + 1.treat#3.plan_surg_proc, eform
lincom 1.treat + 1.treat#4.plan_surg_proc, eform
lincom 1.treat + 1.treat#5.plan surg proc, eform
lincom 1.treat + 1.treat#6.plan_surg_proc, eform
*performing likelihood ratio test for interaction
*fit model for primary analysis
melogit postopinfec i.treat ///
       i.plan surg proc i.asa grade ///
      age spline* haemoglobin spline* creatinine spline* gender ///
      || country:, or
est store B // storing estimates
lrtest A B //interaction test
```

#### Sensitivity analyses: Mortality as a competing risk to postoperative infection

```
mkspline age_spline = age, cubic nknots(3)
mkspline haemoglobin_spline = haemoglobin , cubic nknots(3)
mkspline creatinine_spline = creatinine , cubic nknots(3)

stset time_to_inf, failure(postopinfec_30)
stcrreg i.treat ///
    i.plan_surg_proc i.asa_grade ///
    age_spline* haemoglobin_spline* creatinine_spline* gender /// ///
    ,compete(death_30) vce(cluster country)

*graphing cumulative incidence function
stcurve, at1(treat=1) at2(treat=0) cif
```

# Secondary analysis - estimating the effect of the intervention for participants who undergo surgery (Stata 15)

```
/*Compliance variables required:
c z1: binary indicator equal to 1 if patient is in intervention group and
underwent surgery during the time-frame of the specified outcome, 0 otherwise (and
missing if date of surgery is missing)
c z0 binary indicator equal to 1 if patient is in usual care group and underwent
surgery during the time-frame of the specified outcome, 0 otherwise (and missing if
date of surgery is missing)
reg c z1 treat
predict prob new trt
reg c z0 treat
predict prob std trt
Note in the following command the option "nomleinitial" is required to stop Stata
using a maximum likelihood estimate for initial values. This is not possible due to
the collinearity of the variables in the model. The option "collinear" is required
to supress collinearity check.
*/
bayes, prior ({postopinfec 30: prob std trt}, normal(0.31, 0.27)) ///
             nomleinitial rseed(1234) mcmcsize(100000): ///
             binreq postopinfec 30 prob new trt prob std trt, rd collinear
bayesstats summary ({postopinfec 30:prob new trt} ///
      - {postopinfec 30:prob std trt})
bayesgraph diagnostic {postopinfec 30: prob std trt} {postopinfec 30: prob new trt}
```

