#### Estimating the effect of the intervention for participants who undergo surgery

The main aim of the OPTIMISE II trial is to evaluate whether the intervention improves clinical outcomes compared to control in patients undergoing major elective surgery involving the gastro-intestinal tract. However, in rare instances, surgery may be delayed or cancelled, and so the patient may not undergo surgery before the outcome is collected.

We will therefore conduct a secondary analysis to estimate the effect of the intervention in patients undergo surgery within the follow-up period. This analysis will be conducted for the primary outcome (postoperative infection within 30 days of randomisation), acute cardiac events within 24 hours and 30 days of randomisation.

We will use the method proposed by Bond and White (8) to estimate the effect of the intervention in patients who received surgery. Treatment effects are estimated using a Bayesian method combined with an instrumental variables approach. Full details are provided in the following reference (8). Briefly, this approach involves specifying an informative prior for the effect of receiving the control intervention compared with receiving no surgery. Uninformative priors are used for all other parameters in the model. The approach can provide valid estimates of the effect of intervention in patients who undergo surgery when the prior for the effect of the control intervention vs no surgery is correctly specified.

In this analysis, we will consider patients who do not undergo surgery within the follow up period for the respective outcome as having not undergone surgery. For the outcomes measured at 30 days (postoperative infection within 30 days, acute cardiac event within 30 days), we will count any patient whose date of surgery is 31 days or more after randomisation as not having received surgery. For acute cardiac event within 24 hours of randomisation we will count anyone whose date of surgery is 2 days or more after the date of randomisation as not having received surgery. Patients for whom the date of surgery is missing will be excluded from the analysis (as will patients with missing outcome data).

Our analysis will be based on a difference in proportions between groups; we opted not to use an odds ratio as our effect measure of interest, as we expected the event rate in the no surgery group to be close to zero for some outcomes, which could lead to difficulties when estimating an odds ratio.

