Due to concerns around convergence with small event rates or a low proportion of patients not undergoing surgery, these secondary analyses will not adjust for covariates. In addition, if the event rate across all patients is less than 5% for any outcome, we will not conduct the analysis on this outcome.

The analysis will be conducted using Stata 15. Statistical code to implement the analysis is available in appendix 3.

In order to allow comparison with the intention to treat estimate, we will conduct an additional ITT analysis for each of the outcomes under consideration (postoperative complications within 30 days, acute cardiac events within 24 hours and 30 days) based on a difference in proportions between treatment groups, unadjusted for covariates. This will be based on a generalised linear model with binomial family and identity link.

Our priors will be based on a normal distribution, with means and variances given in Table A for the effect of the control vs no surgery. To assess the sensitivity of our results to choice of prior we will perform two additional analyses using different priors. Main priors are based on the event rates for the subset of patients in the OPTIMISE I trial who were in the control arm and eligible for OPTIMISE II. We will use the default Stata priors for other parameters in the model. All analyses will be conducted using seed 1234 for the random number generator, with 2500 MCMC burn in, and a 100,000 MCMC sample size (102,500 total MCMC iterations).

Table A – Parameters for priors for effect of usual care vs no surgery

| Outcome                          | Prior                    | Mean a | Standard deviation b |
|----------------------------------|--------------------------|-------------------|---------------------------------|
| Postoperative infection          | Main                     | 0.31              | 0.027                           |
| within 30 days of                | Sensitivity 1 (lower)    | 0.28              | 0.027                           |
| randomisation (primary outcome)  | Sensitivity 2 (higher)   | 0.34              | 0.027                           |
| Acute cardiac event              | Main                     | 0.15              | 0.021                           |
| within 30 days of                | Sensitivity 1 (lower)    | 0.12              | 0.021                           |

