# 6. Other analyses, data summaries, and graphs

## Other data summaries

Data on the clinical management of patients during intervention period will be summarised for each treatment group by the mean and standard deviation or median and interquartile range for continuous variables, and the number and percent for categorical variables.

The individual components of each composite outcome (postoperative infection with 30 days of randomisation, acute cardiac event within 24 hours of randomisation, and acute cardiac event

<sup>b Based on OPTIMISE I

within 30 days of randomisation) will be summarised by treatment arm using the number and percent.

Follow up data collected which is not for primary, secondary or process outcomes will be summarised by treatment group by the mean and standard deviation or median and interquartile range for continuous variables, and the number and percent for categorical variables. Differences between groups will not be presented and no statistical tests will be performed on this data.

For details of summaries see draft tables in appendix 5.

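### The Appendix 3 code for the analysis in patients who undergo surgery does not run the Table A prior: it enters 0.27 where Table A gives a standard deviation of 0.027, so the credible interval is too wide when surgery rates differ between arms

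*SAP*

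**What the plan says.** SAP section 5, under the heading on estimating the effect in participants who undergo surgery, adopts a Bayesian instrumental-variable method. It has one informative prior, for usual care versus no surgery on the risk-difference scale; all other priors are uninformative. The SAP says the method is valid "when the prior for the effect of the control intervention vs no surgery is correctly specified".

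The prior is then specified in three places:

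- **Introductory sentence:** "Our priors will be based on a normal distribution, with means and variances given in Table A".
- **Table A:** the spread column is headed as a standard deviation, with the footnote "Based on OPTIMISE I". The main prior for the primary outcome has mean 0.31 and spread 0.027. The two sensitivity priors (means 0.28 and 0.34) also use 0.027.
- **Appendix 3 (Stata 15 code):** "prior ({postopinfec 30: prob std trt}, normal(0.31, 0.27".

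The value 0.27 does not occur in Table A. The SAP does not say whether the second argument of normal() is a standard deviation or a variance.

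**The concern.** One prior has three descriptions that do not agree, and section 5 points to the Appendix 3 code as the implementation of this analysis. If the code is run as printed, the prior is not the pre-specified one.

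This prior is also the one quantity in the model that the data cannot correct. There are two arm means and three coefficients, and the code comments acknowledge the collinearity. Whatever spread is entered for usual care versus no surgery is therefore kept in the posterior. What is at stake is the width of the reported credible interval. The same command is also the only template shown for the two cardiac outcomes and for the sensitivity priors.

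**Working it through.** **Inputs.** From Table A: mean 0.31 and SD 0.027 (infection); mean 0.15 and SD 0.021 (cardiac event, 30 days). From Appendix 3: normal(0.31, 0.27). From SAP section 4: 1251 per arm, 30% versus 25%. Assumed, because the SAP gives no figures: the proportions having surgery, p0 (usual care) and p1 (intervention). The 30% and 25% are applied to patients who have surgery, with no events in the others.

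**1. Is 0.027 a standard deviation?** The SAP says "Main priors are based on the event rates for the subset of patients in the OPTIMISE I trial" but does not give the number of patients. Treating the spread as a binomial standard error:

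- 0.31 × 0.69 / 0.027² = 293 patients
- 0.15 × 0.85 / 0.021² = 289 patients

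These fit one control subset. Read as variances, the same entries would imply 0.31 × 0.69 / 0.027 ≈ 8 and 0.15 × 0.85 / 0.021 ≈ 6 patients. The column heading is therefore right and the word variances is the slip.

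**2. Prior in Table A against prior in the code.** The Table A variance is 0.027² = 0.000729, with 95% range 0.31 ± 1.96 × 0.027 = 0.257 to 0.363.

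| Reading of the code's 0.27 | SD | Variance | Ratio to Table A | 95% range |
|---|---|---|---|---|
| Standard deviation | 0.27 | 0.0729 | 100 | −0.22 to 0.84 |
| Variance | √0.27 = 0.52 | 0.27 | 370 | −0.71 to 1.33 |

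Even if Table A's 0.027 were a variance, the code would be 0.27 / 0.027 = 10 times too large.

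**3. How the spread reaches the treatment effect.** Let a be the risk without surgery, and let b0 and b1 be the effects of usual care and intervention, each versus no surgery. The arm means are μ0 = a + b0·p0 and μ1 = a + b1·p1. Eliminating a:

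b1 − b0 = (μ1 − μ0)/p1 + b0·(p0/p1 − 1)

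The data do not update b0, so

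posterior SD = √[ var(μ1 − μ0)/p1² + (SD_prior × (p0/p1 − 1))² ]

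**4. Interval width.** At 98%/95% the arm means are 0.98 × 0.30 = 0.294 and 0.95 × 0.25 = 0.2375.

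- SE(μ1 − μ0) = √[(0.294 × 0.706 + 0.2375 × 0.7625)/1251] = 0.01763; divided by 0.95 this is 0.01855.
- The multiplier on the prior is 0.98/0.95 − 1 = 0.0316.

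Posterior SD in percentage points:

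| Surgery rates (usual care/intervention) | Table A | Code as SD | Code as variance | Increase |
|---|---|---|---|---|
| 98%/98% | 1.81 | 1.81 | 1.81 | 0% |
| 98%/97% | 1.82 | 1.84 | 1.90 | about 1% to 4% |
| 98%/95% | 1.86 | 2.04 | 2.48 | about 10% to 33% |

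**5. Point estimate and sensitivity priors.** At 98%/95%, (0.2375 − 0.294)/0.95 = −5.95 points. Adding b0 × 0.0316 for prior means 0.28, 0.31 and 0.34 gives −5.06, −4.97 and −4.87 points. The prior SD does not enter this expression, so the three values are the same under Table A and under either reading of the code.

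**Simulation check.** A run of 400,000 draws at 98%/95%, with 30% and 25% taken as the overall arm means, gave a mean effect of −4.28 points under all three spreads. The 95% half-widths were 3.68 (Table A), 4.04 (code as SD) and 4.88 points (code as variance).

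**The case against.** Several points on the other side stand. The analysis is secondary, unadjusted and was added in SAP version 2.0. The SAP expects surgery to be cancelled or delayed only rarely, and randomisation takes place shortly before the operation, so surgery rates are likely to be high and similar in both arms. The prior spread then scarcely matters. The factor of 370 and the larger increases depend on the second argument being a variance, which the SAP does not state. Only one command is printed, for one outcome and its main prior. Underscores are also missing from this code block in the machine-read text, so a lost digit cannot be ruled out, although nothing shows that one was lost.

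None of this reconciles 0.27 with 0.027, and the code cannot be set aside as illustration, since section 5 relies on it to implement the analysis.

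A reader might infer two stronger things. The first is that the treatment effect is identified only by this prior, so that a diffuse entry ruins it. The formula does not support that: the prior acts only through p0/p1 − 1, and with equal surgery rates the data alone identify the contrast. What becomes vague is the nuisance effect of usual care versus no surgery. The second is that sensitivity shifts of 0.03 become meaningless beside a prior SD of 0.27 or 0.52. Step 5 shows otherwise: each shift moves the estimate by about 0.09 points whatever the spread.

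**Conclusion.** Wrong as written; a minor to should-fix correction to a secondary analysis. The code does not carry the Table A prior under any reading, and the sentence introducing Table A contradicts its column heading. Point estimates and the differences between sensitivity priors are unaffected. The credible interval for the effect in surgery patients is too wide, by nothing when surgery rates are equal and by about 10% to 33% at 98%/95%. The primary and ITT analyses are unaffected.

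These sizes rest on assumed surgery rates, on 1251 patients per arm with 30% and 25% infection among surgical patients, on diffuse priors for the other coefficients, and on a normal approximation. The lower and upper ends correspond to 0.27 being a standard deviation or a variance.

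**What to change.** - **Code:** first confirm the printed digit in the original PDF. Then make the code match Table A: enter 0.027² = 0.000729 if the second argument of normal() is a variance, or 0.027 if it is a standard deviation. If it is a variance, merely restoring the missing zero would leave it 0.027 / 0.000729 = 37 times too large.
- **Other outcomes:** treat the cardiac priors the same way. On the variance convention these are 0.021² = 0.000441 (30 days) and 0.01² = 0.0001 (24 hours).
- **Convention:** state in Appendix 3 which one the code uses.
- **Text:** in the sentence before Table A, change variances to standard deviations.

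The cost is one line of code, one comment and one word of text. No design choice or other analysis changes.

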# Appendix 4: Missing data sensitivity analysis

#### Rubin's Rules

Estimates and standard errors from the analysis of imputed data sets will be combines using Rubin's rules (7). These are described in an easy to understand format in (9).

For m imputed data sets with treatment estimates  $\hat{Q}_i$  with variances  $\widehat{var(Q_i)}$  the combined treatment estimate, will be given by  $\bar{Q}$ , the mean of the m estimates from the imputed data sets:

$$\bar{Q} = \frac{1}{m} \sum_{i=1}^{m} \hat{Q}_i.$$

The estimate of the variance of the overall imputed variance will be calculated by:

$$\operatorname{var}(\bar{Q}) = \bar{U} + \left(1 + \frac{1}{m}\right)B$$

Where 
$$\overline{U}=rac{1}{m}\; \sum_{i=1}^{m} \widehat{var(Q_i)}$$
 and  $B=rac{1}{m-1}\sum_{i=1}^{m} \widehat{(Q_i-ar{Q})^2}$  .

Confidence intervals and p-values will be from a t distribution with degrees of freedom given by:

$$df = (m-1)(1 + \frac{m\overline{U}}{(m+1)B})^{2}$$

#### Example Stata code for the missing data sensitivity analysis

```
mkspline age spline = age, cubic nknots(3) displayknots // creating splines
mkspline haemoglobin_spline = haemoglobin, cubic nknots(3) displayknots
mkspline creatinine spline = creatinine, cubic nknots(3) displayknots
local m = 10 // number of imputations
foreach p0 in 0.15 0.2 0.25 0.3 0.35 0.4 \{ // proportion of events in u.c group
       foreach d1 in -0.1 -0.05 0 0.05 0.1 { // difference in prop between groups
              local p1 = `p0' + `d1' // proportion of events in intervention group
             preserve
*Imputing
             forvalues i = 1 (1) m' {
                     qui gen _`i'_postopinfec_30 = postopinfec_30
                     forvalues t = 0 (1) 1 {
                            aui{
                            gen miss_order_`i'_`t' = runiform(0,1) ///
                            if treat == `t' ///
                     & postopinfec 30 ==. // generating random variable to sort on
                            sort miss_order_`i'_`t' // sorting
                            gen miss_no_`i'_`t' =_n if treat ==`t' ///
                            & postopinfec 30 ==.
                            qui count if treat == `t' & postopinfec_30 ==.
                            replace _`i'_postopinfec_30 = 1 ///
if miss_no_`i'_`t' < `p`t''*r(N) ///</pre>
                            & treat == `t' & postopinfec 30 ==.
                            replace _`i'_postopinfec_30 = 0 ///
```

```
if miss_no_`i'_`t' >= `p`t''*r(N) ///
   & treat ==`t' & miss_no_`i'_`t' !=. ///
                            & postopinfec 30 ==.
                   }
*Analysing imputed data sets
             forvalues i = 1 (1) 10 {
                    qui melogit _`i'_postopinfec_30 i.treat ///
                           i.plan_surg_proc i.asa_grade ///
                    age_spline* haemoglobin_spline* creatinine_spline* ///
                     i.gender || country:, or
                    scalar est`i'= _b[1.treat] // storing treatment estimate
                    scalar var`i' = (_se[1.treat])^2 // storing standard error
             }
*Combining estimates
             scalar q bar = (est1 + est2 + est3 + est4 + est5 + est6 + est7 + //
              est8 + est9 + est10)/m'
             *Combining variances
             scalar u bar = (var1 + var2 + var3 + var4 + var5 + var6 + var7 + ///
              var8 + var9 + var10)/`m'
             scalar B = ((est1-q_bar)^2 + (est2-q_bar)^2 + (est3-q_bar)^2 ///
             +(est4-q bar)^2 + (est5-q bar)^2 + (est6-q bar)^2 + ///
              (est7-q_bar)^2 + (est8-q_bar)^2 + ///
              (est9-q bar)^2 + (est10-q bar)^2)/(m'-1)
             scalar varQ = u bar+ (1+(1/m'))*B
             scalar imp se = varQ^0.5
             di "se: " imp_se
             *Calculating degrees of freedom
             local df = (m'-1)*(1+(m'*u_bar/((m'+1)*B)))^2
             *Calculating p valaue
             local p = 2*(1-t(^df', abs(q_bar/imp_se)))
             *Confidence limits
             local ul = q_bar + imp_se*invt(`df', 0.975)
             local ll = q_bar - imp_se*invt(`df', 0.975)
             *Displaying results:
             di "Event rate amongst usual care group with missing data: `p0'"
             di "Event rate amongst intervention group with missing data: `p1'"
             di "Estimated odds ratio for treatment effect (95% CI): ///
             " exp(q_bar) " (" exp(`ll') ", " exp(`ul') ")"
             restore
      }
}
```

